4.8 Rationale for Allogeneic Myeloma Vaccine

In multiple myeloma, donor lymphocyte infusions (DLI) have been able to induce prolonged remissions in patients who relapsed after allogeneic transplantation.³⁹ This approach demonstrates the efficacy of immune mediated anti-tumor effect in myeloma. We have been able to measure tumor specific T cell responses in a recent trial using an autologous vaccine in the setting of a stem cell transplant. However, significant barriers still exist that prevent us from maximizing vaccine-mediated anti-tumor efficacy. Results from both pre-clinical and clinical studies have demonstrated that tumor vaccines work

best in the setting of minimal residual disease. A possible explanation for these findings is the immunosuppressive effects of advanced tumors in tumor-bearing hosts. Specifically, the increase in VEGF levels that result in impaired dendritic cell function, changes in ζ -chain signaling on the T cell receptor resulting in global immunosuppression, the induction of myeloid suppressor cells exerting an inhibitory immune effect via nitric oxide and arginase-dependent pathways and the development of antigen-specific tolerance induction resulting in a skewing from a positive Th1 CD4 response to an inhibitory Th2 response.

These findings have enabled us to identify putative targets to improve the underlying immune responsiveness of the host in an effort to augment the efficacy of tumor-specific vaccine strategies in an immune responsive host, and to impart an immune-mediated anti-tumor effect on chemo-resistant tumors, that underscore the ability of active immunotherapy to exert its anti-tumor effect through non-cross-reactive mechanisms. Taken together, these findings provide a strong rationale for studies that integrate tumor vaccines into a setting in which prior therapy achieved its maximal anti-tumor benefit.

We have tested the immunomodulatory role of lenalidomide on pneumococcal vaccine (Prevnar) responses in a recently conducted clinical trial (described above) in patients with relapsed myeloma²². Ultimately the data demonstrated that lenalidomide augments *in vivo* immune responses in patients with advanced/relapsed multiple myeloma, which provides the rationale for utilizing this drug in combination with cancer vaccines to augment anti-tumor efficacy.

Most patients achieving a CR still go on to relapse¹⁴. However, the depth and duration of CR may play an important role in disease prognosis, and higher CR has been shown to correspond with improved survival. The potential benefit of tumor vaccine may be best seen in the setting of minimal residual disease (MRD), where tumor induced tolerogenic mechanisms may be less relevant, and may be an effective mechanism of achieving a deeper remission such as stringent CR when not already in stringent CR, or molecular CR.

We will study the effect of the tumor vaccine in patients achieving at least a near complete remission (nCR), as well as a complete remission (CR) with a lenalidomide based regimen. The goal of the study will be to improve the clinical responses in patients with near complete remission (nCR) or complete remission who are also minimal residual disease positive (MRD+), and to determine whether the allogeneic myeloma vaccine confers a PFS advantage upon patients treated with allogeneic myeloma vaccine in combination with lenalidomide (with or without Prevnar vaccine) as compared to a non-vaccine control arm with patients on lenalidomide alone. The effect of adding Prevnar to the allogeneic myeloma vaccine and lenalidomide combination will also be explored.

Since administration of corticosteroids can dampen immune responses, patients will discontinue dexamethasone or other steroids at least one month prior to receiving the first vaccine, and must not show evidence of progressive disease as defined by the International Uniform Response criteria⁴⁷, prior to being started on the trial. The adverse

effects and significant morbidity from long term use of corticosteroids are well described, and this trial will give us an excellent opportunity to explore novel treatment strategies in a 'steroid free' regimen with a goal to improve the depth of response and have a low toxicity profile.

The incorporation of the Prevnar vaccination in our earlier study had a dual purpose. We were able to measure the efficacy of the vaccine by examining both the humoral, as well as cellular responses to Prevnar; and we uncovered a potential therapeutic effect of Prevnar vaccine in our earlier study. Specifically, the ability of Prevnar to prime T cell responses targeting HB-EGF (heparin binding epidermal growth factor), a cell adhesion molecule expressed on a significant percentage of myeloma cells.^{22, 23}

We believe that the data support the efficacy of lenalidomide in augmenting *in vivo* immune responses in patients with multiple myeloma, and thus warrant the investigation of lenalidomide in combination with the allogeneic myeloma vaccine without the potentially confounding effect of Prevnar. However, to confirm that clinical benefits are primarily due to the effect of allogeneic myeloma vaccine alone, there is an additional comparison arm consisting of allogeneic myeloma vaccine along with Prevnar, in combination with lenalidomide which was the composition of the vaccine in our Phase I trial.

5 STUDY OBJECTIVES AND ENDPOINTS

5.1 Study objectives:

Primary:

- To compare the 2-year progression free survival of patients with multiple myeloma in a near complete remission (nCR) or complete remission (CR) who are also minimal residual disease positive (MRD+), treated with an allogeneic myeloma vaccine in combination with lenalidomide (with or without Prevnar vaccine) versus placebo in combination with lenalidomide.

Secondary:

- To compare the 2-year progression free survival for those treated with or without Prevnar in addition to an allogeneic myeloma vaccine and lenalidomide
- Determine rate of conversion of nCR to true CR
- Determine rate of conversion of MRD positivity to MRDnegativity
- Determine time to response
- Determine the progression free survival at 3 and 5years
- Evaluate toxicity of the allogeneic myeloma vaccine
- Measure tumor specific immunity and correlate with systemic immunity

6 INVESTIGATIONAL PLAN

6.1 Overall design:

[figure not shown]
Patients with newly diagnosed or relapsed/refractory multiple myeloma (NDMM or RMM) in CR or nCR who meet appropriate criteria will be eligible for enrollment.

Specifically:

[figure not shown]
- Patients with NDMM who have completed 6 cycles of treatment with any lenalidomide containing regimen (e.g. KRD, VRD, Rd, BiRD or R alone) and who have been in CR or nCR for ≥ 3 months.
- Patients with MM who have undergone ASCT will only become eligible ≥ 12 months following date of cell infusion, will have been on lenalidomide maintenance for ≥ 6 cycles prior to enrollment, and continue to meet criteria for CR or nCR for ≥ 3 months.
- Patients with RMM will need to have completed at least 6 cycles of current therapy with a lenalidomide containing regimen, and be in CR or nCR for ≥ 3 months.
- All patients must be MRD positive at 10^{-4} by NGS sequencing at enrollment

Eligible patients who go on to enroll will be randomized in a 1:1:1 fashion to one of three arms. All patients will continue on a standard dose of lenalidomide (15mg daily, to be adjusted as clinically necessary), given on days 1 – 21 of a 28 day cycle. Patients on the myeloma vaccine arm will receive injections with an allogeneic myeloma vaccine administered intradermally on day 14 of cycles 1, 2, 3, 6 and annually for a minimum of 36 months in addition to lenalidomide unless otherwise clinically indicated, or until progression. Patients on myeloma plus Prevnar vaccine arm will receive injections of both allogenic myeloma vaccine, intradermally, and Prevnar vaccine, intramuscularly, on day 14 of cycles 1, 2, 3, 6, and annually for a minimum of 36 months in addition to lenalidomide unless otherwise clinically indicated, or until progression. Patients on the myeloma vaccine placebo arm will receive myeloma vaccine placebo on the same schedule as allogeneic myeloma vaccine. If assigned to either of the two arms that do not include Prevnar, then patients will receive placebo in lieu of Prevnar on the same schedule. The placebo will be saline. The study schema is shown below:

SCHEMA

Vaccination Schedule

Allogeneic Myeloma Vaccine or placebo administration – in months: 1, 2, 3, 6, 12, 24, and 36
 Prevnar or Prevnar placebo administration – concurrent with myeloma vaccine administration
 MRD testing – enrollment, 6 mo, 12 mo, annually for the duration of study

6789

6.1.1 Registration on Study and Randomization

[figure not shown]
At registration, patients will have the baseline evaluations listed in Sections 2 and 7. Once eligibility requirements are met, the patients will proceed to bone marrow biopsy with cytogenetics and FISH analysis, and/or GEP assessment via myPRS, if this information is not already available at diagnosis, or on recent testing. Randomization in a 1:1:1 fashion will occur after screening and eligibility requirements have been met, and bone marrow biopsy obtained if needed. The primary criteria for stratification will be:

- Near Complete Remission vs Complete Remission (nCR vCR)
- Prior autologous stem cell transplant vs no prior autologous stem cell transplant

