7 SCREENING AND ELIGIBILITY

Subjects must meet the following inclusion/exclusion criteria to be eligible for the study.

7.1 Inclusion Criteria:

- Myeloma eligibility criteria are the following:
 - Near complete remission (nCR) for ≥ 3 months defined as no measurable M-spike, and a positive serum immunofixation
 - For patients with a light chain only myeloma, they will be deemed to be in a CR if they meet criteria for CR by International Myeloma Working Group (IMWG) consensus criteria2016.
 - For patients with a light chain only myeloma that meet criteria for Very Good Partial Response (VGPR) by IMWG consensus criteria 2016 and are IFE –ve (negative serum immunofixation), they will be considered to be in a near complete remission (nCR).
 - Or complete remission (CR) (no measurable M-spike, immunofixation negative and bone marrow clonal plasma cells <5%)
 - NDMM or RMM in nCR or CR having completed a minimum of 6 cycles of a lenalidomide based regimen for a minimum of ≥ 3 months
 - NDMM or RMM a patients who have been off corticosteroids for ≥ 4 weeks
 - Patients with NDMM or RMM who have had autologous stem cell transplant are eligible, but must be ≥ 12 months from transplant
 - All patients must be MRD positive at 10^{-4} or greater by NGS sequencing at enrollment
- All patients must be currently taking Revlimid at screening.
- Age >18 years
- ECOG performance scores 0-2
- History of measurable serum or urine M protein or free light chains
- Life expectancy greater than 12 months
- Corrected serum calcium < 11 mg/dL, and no evidence of symptomatic hypercalcemia
- Serum creatinine < 2 mg/dl
- ANC $>1000/\mu\text{L}$
- Platelet $>100,000/\mu\text{L}$
- Total bilirubin $\leq 1.5 \times \text{ULN}$
- AST (SGOT) and ALT (SGPT) $\leq 3 \times \text{ULN}$.
- Ability to comprehend and have signed the informed consent.
- Have previously agreed to continue on maintenance therapy with lenalidomide concurrent with vaccine administration until disease progression, or clinical indication to cease therapy.
- All patients must be willing and able to comply with the requirements of the REMS® program as directed by their providers.
- All study participants will have been registered into the mandatory Revlimid REMS® program as per standard of care, prior to enrollment.
- Females of reproductive potential must adhere to the scheduled pregnancy testing as required in the Revlimid REMS® program.

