- Females of childbearing potential (FCBP)† must have a negative serum or urine pregnancy test with a sensitivity of at least 50 mIU/mL within 10 – 14 days prior to starting lenalidomide with each cycle (prescriptions must be filled within 7 days) and must either commit to continued abstinence from heterosexual intercourse or begin TWO acceptable methods of birth control, one highly effective method and one additional effective method AT THE SAME TIME, at least 28 days before taking lenalidomide, as per standard of care. FCBP must also agree to ongoing pregnancy testing. Men must agree to use a latex condom during sexual contact with a FCBP even if they have had a successful vasectomy. See **Appendix 5: Risks of Fetal Exposure, Pregnancy Testing Guidelines and Acceptable Birth Control Methods**.
- Able to take prophylactic anticoagulation (aspirin 81 or 325 mg/daily or, for patients intolerant to ASA, warfarin or low molecular weight heparin).

† A female of childbearing potential is a sexually mature woman who: 1) has not undergone a hysterectomy or bilateral oophorectomy; or 2) has not been naturally postmenopausal for at least 24 consecutive months (i.e., has had menses at any time in the preceding 24 consecutive months).

7.2 Exclusion Criteria:

- Disease progression after stopping corticosteroids as defined as the appearance of a detectable serum or urine M-spike, or an absolute increase of >10 mg/dl between involved and unininvolved light chains, in the absence of measurable serum or urine M-protein.
- Patients who are MRD negative by NGS at screening.
- Patients with a known diagnosis of POEMS syndrome, plasma cell leukemia, CNS involvement, non-secretory myeloma and amyloidosis
- High-risk myeloma defined by presence of at least one of the following defining features on initial diagnostic, or most recent bone marrow biopsy:
 - High risk chromosomal translocations by FISH: t(4;14), t(14;16), t(14;20),
 - del(17p), del(1p), amplification 1q.;
 - MyPRS GEP-70 or SkylineDx high risk signature either from diagnosis or at time of registration for the study;
 - LDH > 300 U/L at diagnosis;
 - Relapse from prior therapy within 12 months.
- HIV disease, active infection requiring treatment with antibiotics, anti-fungal or anti-viral agents within 2 weeks of enrollment would be excluded from the study.

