11.2 Statistical Analyses

The efficacy and safety analysis populations will include all patients that received at least one dose of their assigned treatment. The primary analyses will compare the control arm with the pooled vaccine arm. Secondary analyses will compare the two vaccine arms to one another and to the control arm.

Demographic and disease characteristics will be summarized overall and within each treatment group using medians and ranges for continuous variables and counts and proportions for categorical variables.

The primary outcome (PFS) is defined as the time from randomization until progression or death. Individuals who do not have an event will be censored at the date of last assessment. Kaplan-Meier estimates of the survival function will be used to compare the two treatment groups graphically as well as to provide estimates of the median PFS and the proportion who have progressed at key time points (e.g. 1-, 2-, and 3-years) with 90% confidence intervals. Log-rank tests will be used to compare the treatment groups and Cox proportional hazards models will be used to examine the effects of specific risk factors of interest and their interaction with treatment (e.g. vaccine by MRD status interactions). If the proportional hazards assumption is violated, the piecewise proportional hazards models or other semi-nonparametric approaches will be used. Key secondary endpoints include conversion from “near CR” (M-spike at or below 0 but IFE positive), to “true CR” (IFE negative), and conversion from MRD positive status to MRD negative status. These and other time to event outcomes including will be analyzed in a similar manner to the primary outcome as well as with competing risk models to account for death or progression.

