Tumor immunology assessments will be made at baseline and on day 14 of cycles 3, 6, and 12 (the 1-year assessment). At each time point, graphical (e.g. boxplots over time, spaghetti plots) and numeric (e.g. median, range, proportion) summaries will be used to explore the continuous (e.g. T cell populations) and binary (e.g. tumor specific immunity) outcomes. If appropriate, transformations (e.g. log) will be used to address skewness in the data. Cross-sectional comparisons will be made using t-tests, Kruskal-Wallis tests, or linear regression and Chi-squared tests, Fisher’s exact test, or logistic regression for continuous and categorical outcomes, respectively. Generalized estimating equations and mixed effects models will be used to formally model the behavior over time and compare treatment groups and/or risk factors while adjusting for repeated measurements within each individual. The association between baseline tumor measurement as well as changes in tumor measurements over time and clinical outcomes will be assessed using Cox proportional hazards models.

Toxicity will be scored using NCI CTC Version 4.0 for toxicity and adverse events. All toxicities will be summarized overall, by treatment group, and within subgroups of interest (e.g. true CR status, MM type). The number of toxicities and number of affected patients will be tabulated by type, grade, and relatedness to study treatment (overall and for each treatment). In addition to counts and proportions, the toxicity rates will be modeled and compared between treatment groups and subgroups of interest using Poisson regression or Negative Binomial regression, as appropriate.

11.3 Toxicity Stopping Guidelines:

The proportion of unacceptable toxicities will be continuously monitored in each arm separately. Unacceptable toxicities include hematologic toxicities of lenalidomide: low neutrophils (ANC <1000) and low platelets (<50K), for which we would hold the vaccine administration, as well as vaccine related toxicities which include: grade 3/4 local reactions (erythema, swelling, pain) and systemic symptoms (fevers, rash) (Refer to **7.6.1** and **7.6.2** for guidelines on attribution of toxicities).

Unacceptable toxicities as scored using **NCI CTCAE V5.0** include:

- Any laboratory or clinical organ dysfunction \geq Grade 3
- Abnormalities of coagulation (prolonged prothrombin, partial thromboplastin and clotting times \geq Grade 3)
- Autoimmune disease reactivation or development \geq Grade 2

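### The primary log-rank comparison names no strata or covariates, so it uses neither its own two randomisation factors nor newly diagnosed versus relapsed disease; a prespecified adjusted hazard ratio would protect the estimate

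*Combined protocol and SAP*

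**What the plan says.** Section 6.1 admits "Patients with newly diagnosed or relapsed/refractory multiple myeloma (NDMM or RMM) in CR or nCR" and sets entry conditions by disease setting, so the setting has to be known before randomisation. Section 6.1.1 names two stratification factors: nCR versus CR, and "Prior autologous stem cell transplant vs no prior autologous stem cell transplant". Transplant history does not stand in for disease setting, because Section 7.1 states that "Patients with NDMM or RMM who have had autologous stem cell transplant are eligible".

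For the analysis, Section 11.2 says "Log-rank tests will be used to compare the treatment groups" and lists no strata. It adds that "Cox proportional hazards models will be used to examine the effects of specific risk factors of interest and their interaction with treatment". Those factors are not named, and the one example is MRD status. Disease setting is not named anywhere as a stratification factor, covariate or efficacy subgroup. A myeloma-type subgroup appears once in Section 11.2, undefined and only for toxicity summaries. Appendix 1 refers the reader to an Appendix IV for stratification indicators, but Appendix 4 contains the toxicity criteria.

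**The concern.** With 18 controls against 36 vaccinated patients, a baseline factor left to chance can differ noticeably between arms. If that factor predicts progression, the unadjusted hazard ratio is pulled towards or away from the vaccine, and nothing in the plan corrects it. Omitting a prognostic factor also weakens the average unadjusted effect somewhat, even when the arms are balanced. The plan stratifies the randomisation on two factors that its analysis does not mention, and it leaves out a third that its own eligibility rules separate. Adjustment chosen after the data are seen would be open to dispute, and this trial has a single small efficacy analysis.

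**Working it through.** **Inputs from the plan.** Section 11.1: 18 versus 36 patients, control median 18 months, HR 0.4199, two-sided alpha 10%, 24 months of accrual, at least 36 months of follow-up, 1% loss per year, stated power 80%.

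**Assumed inputs (not in the plan for this population).** RMM share 20-50%. RMM-versus-NDMM hazard ratio 1.5 to 2.84. The upper value comes from two studies in Section 4.2. The relapsed-setting median time to progression of 11.1 months gives ln 2/11.1 = 0.0624 per month. The newly diagnosed 2-year PFS of 59% without transplant gives -ln 0.59/24 = 0.0220 per month. The ratio is 2.84.

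**Step 1: reproduce the stated power.** With exponential PFS, the chance of an observed event is λ/(λ+δ) × (1 - exp(-(λ+δ)u)), averaged over follow-up u from 36 to 60 months, with δ = 0.01/12.
- Control: λ = ln 2/18 = 0.0385, probability 0.825, events 18 × 0.825 = 14.85.
- Vaccine: λ = 0.4199 × 0.0385 = 0.0162, probability 0.5276, events 36 × 0.5276 = 18.99.
- Total about 34 events. SE(log HR) = √(1/14.85 + 1/18.99) = 0.346.
- Power = Φ(0.868/0.346 - 1.645) = Φ(0.86) = 80.5%. A simulated log-rank test gives 80.9%. The plan's 80% stands.

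**Step 2: chance imbalance.** With K RMM patients among 54, the number k in the control arm is hypergeometric, and the gap is k/18 - (K-k)/36. For K = 16 (30%), a gap of at least 20 points means k ≤ 2 (2/18 versus 14/36, -28 points) or k ≥ 8 (8/18 versus 8/36, +22 points).

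| RMM share | Probability of a gap of at least 20 points |
|---|---|
| 20% | 8% |
| 30% | 12% |
| 40% | 15% |
| 50% | 15% |

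**Step 3: effect on the estimate.** Simulated at true HR 0.4199, 2,000 trials per case (Monte Carlo SE about 1 point). The three figures in each cell are for an RMM hazard ratio of 1.5 / 2.0 / 2.84.

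| RMM control vs vaccine | Unadjusted HR | HR adjusted for NDMM/RMM | Log-rank power |
|---|---|---|---|
| 3/18 vs 13/36 (-19 points) | 0.46 / 0.49 / 0.55 | 0.41 / 0.41 / 0.41 | 72 / 64 / 52% |
| 8/18 vs 8/36 (+22 points) | 0.38 / 0.37 / 0.36 | 0.41 / 0.41 / 0.40 | 86 / 88 / 91% |

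In the second case the log-rank test's null rejection rate is 12 / 12 / 15%; adjustment returns it to about 10%. Part of the movement in the first case is attenuation rather than imbalance: at 50% RMM, the unadjusted HR averaged over all splits is already 0.43 at 2.0 and 0.46 at 2.84.

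**Step 4: average power over all splits (40% RMM).**

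| RMM hazard ratio | Log-rank | Cox with NDMM/RMM, nCR/CR and transplant |
|---|---|---|
| 1.5 | 80% | 80% |
| 2.0 | 76% | 79% |
| 2.84 | 71% | 78% |

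Another run at 1.5 gave 78.9% versus 77.7%, so the difference there is zero or a small loss. A log-rank test stratified by NDMM/RMM gives 78-80% power across RMM shares of 30% and 50% and all three hazard ratios.

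**Step 5: type I error over all splits (nominal 10%).** Unstratified log-rank 10-11%; log-rank stratified by NDMM/RMM about 9-11%; three-covariate Cox Wald test about 11-13%.

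**The case against.** The strongest reply is that the size rests on assumptions. The documents give neither the RMM share nor its prognostic effect here. The 2.84 sets one study's time to progression against another's PFS. This trial also narrows the contrast: everyone is in nCR or CR after at least six lenalidomide cycles, and high-risk disease, including "Relapse from prior therapy within 12 months", is excluded. The true value is probably lower, and at 1.5 there is no power to recover. Shifts of the size in Step 3 are also small beside an SE of about 0.35 on the log HR. Other baseline factors could compete for the same place, and the Cox sentence in Section 11.2 leaves room to include disease setting. All of this stands and limits the weight of the point. It does not close the gap, because the Cox sentence commits to nothing and even the two randomisation factors are missing from the stated comparison.

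A reader might infer four stronger things that the documents do not support.
- That the primary test is biased: randomisation keeps its overall type I error at 10-11%.
- That the 80% power is wrong: it reproduces.
- That disease setting should become a third stratification factor: that makes 8 cells averaging 54/8 = 6.75 patients.
- That an adjusted hazard ratio reported beside the log-rank test raises the trial's power: the deciding test, and so its power, would be unchanged.

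**Conclusion.** The point holds as an issue of estimation and modest efficiency, not of validity. The stated primary comparison ignores both randomisation factors and a baseline distinction known at entry. A gap of at least 20 points in RMM share can be expected in about 8-15% of such trials if 20-50% of patients are RMM, and the unadjusted HR would then drift from 0.42 to roughly 0.46-0.55 or 0.36-0.38, depending on direction and prognostic strength. The average power forgone is about 0 points at an assumed prognostic HR of 1.5, 2-3 points at 2.0 and 6-7 points at the upper bound of 2.84. The Step 4 Cox figures treat nCR/CR and transplant as non-prognostic; if they are prognostic, adjusting for them would do more. The case for change rests mainly on protecting the reported effect estimate at almost no cost.

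**What to change.** Leave the randomisation as it is. In Section 11.2:
- Keep the log-rank test as the decision test.
- Prespecify that the reported treatment HR, with its 90% confidence interval, comes from a Cox model with treatment, NDMM/RMM, nCR/CR and prior transplant, and that its Wald p-value is supportive only.
- If a test that gains power from disease setting is wanted, name a log-rank test stratified by NDMM/RMM in advance, in place of the unstratified one.
- Define NDMM/RMM for every patient. The transplant entry path in Section 6.1 does not state the setting. Confirm too that the case report form captures it; that it is recorded is inferred here from eligibility and the baseline history and diagnosis items.
- Correct the Appendix 1 pointer to a stratification list.

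The cost is a few sentences. The statistical price is three parameters beyond treatment on about 34 events, and a Wald test that rejects at about 11-13% under the null at a nominal 10%, which is why it should not decide the trial. If disease setting turns out not to matter, about one point of power is lost in the adjusted model and none in the decision test.
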